5.0 Introduction

5.1 Background

Atrial fibrillation (AF) is the most common sustained cardiac arrhythmia, with a prevalence of between 0.9% and 2.5% in the general population and an increasing incidence with age.^{2,3} This arrhythmia is associated with an increased risk of thromboembolic complications and in particular of ischemic stroke. The rate of this complication varies from fewer than 2 to more than 10 strokes per 100 patient-years without antithrombotic therapy.^{4,5} The stroke risk increases in the presence of cardiovascular diseases, such as rheumatic mitral stenosis, or prosthetic cardiac valves. Furthermore, patients with non-valvular AF, a history of previous thromboembolism, advanced age, hypertension, diabetes mellitus, and heart failure have an increased risk of stroke.⁶ Thromboembolic complications generally result from left atrium thrombi, the left atrial appendage (LAA) being the most common source of thrombus formation, with an incidence of 91% in patients with non-valvular AF.^{6,7} The pathogenesis of LAA thrombi has not been fully elucidated, but the relative stasis of the blood within the appendage, due to its anatomy and altered function during AF (reduced contraction, filling dynamics), is thought to play a major role.⁸

Adjusted-dose warfarin is highly effective in preventing stroke, and reduces risk by 62% versus placebo in patients with non-valvular AF;⁹ however, it increases the risk of major bleeding by 1.2% per year.⁶ The absolute reduction in stroke risk is reported to be 2.7% per year for primary prevention and 8.4% per year for secondary prevention.⁹

Although the efficacy of warfarin in preventing stroke in AF patients has been clearly demonstrated, oral anticoagulation is still underused in clinical practice for several reasons. Firstly, oral anticoagulation therapy carries a substantial risk of hemorrhage; this could be underestimated in clinical practice, considering the restrictive selection criteria used in randomized trials, in which patients with lower risk of bleeding are often enrolled. For example, in the SPINAF trial only 7% of the 7982 patients initially screened were enrolled.¹⁰ Moreover, the risk of hemorrhage is strictly related to the patient's age. Indeed, the incidence rate of major hemorrhage has been found to rise from 1.5 per 100 patient-years for patients younger than 60 years to 4.2 per 100 patients-years for patients older than 80 years (hazard ratio of 2.7).¹¹ In a meta-analysis of major randomized trials of oral anticoagulation therapy, the mean age of patients was 69 years, and only 20% of participants were older than 75 years.⁹

By contrast, in clinical practice this latter group of patients represents more than 50% of the population that needs to be treated with anticoagulation therapy.⁷ The second reason for the underuse of oral anticoagulation is that this therapy, specifically warfarin, is associated with restrictions in everyday life, as it requires frequent monitoring of the INR level in order to adjust the therapeutic dosage. Finally, it is well known that a considerable percentage of patients are unable to comply with oral anticoagulation therapy. In warfarin-treated patients, discontinuation of this therapy occurs at rates of up to 38% a year and approximately 50% of strokes occur during inadvertent therapeutic lapses or in subjects who temporarily or permanently cease therapy.⁸

The benefit of oral anticoagulation is more substantial in patients who are at high risk for stroke. Despite this benefit, a considerable portion of these patients may have relative or absolute contraindications to warfarin treatment that prevent use of the recommended anticoagulation therapy. Indeed, it has been reported that 46% of elderly Medicare beneficiaries have contraindications to warfarin, such as previous hemorrhage, blood dyscrasias, and renal or hepatic disease.¹² Recently, new medications for oral anticoagulation therapy have been developed and approved for use. Two recent clinical trials compared the use of rivaroxaban (ROCKET AF study) and dabigatran (RE-LY study) with warfarin in patients with AF. In the ROCKET AF Study, rivaroxaban was non-inferior to warfarin for prevention of stroke and non-CNS embolism, with similar rates for adverse events and bleeding.¹³ In the RE-LY Study, dabigatran compared with warfarin was associated with lower rates of stroke and systemic embolism but similar rates of major hemorrhage.¹⁴ The net clinical benefit of new oral anticoagulants (dabigatran, rivaroxaban, and apixaban) versus no treatment in a “real world” AF population was presented in a recently published study. Using a modeling analysis based on a nationwide cohort study, Banerjee, et al found that when the risk of bleeding and stroke are both high, these new anticoagulants appear to have a greater net clinical benefit compared to warfarin.¹⁵ The management of these patients remains challenging; however, and alternative methods of treatment to reduce embolic stroke need to be considered.

Since the late 1990s, catheter ablation has offered a minimally-invasive, non-pharmacological therapeutic option to patients with AF. Over a short period of time this procedure has become a more commonly performed ablation technique that is used throughout the world in appropriately selected patients. Haïssaguerre, et al demonstrated that the majority of AF is initiated by ectopic foci found primarily in the pulmonary veins;¹⁶ however, different approaches have since been developed to electrically confine the triggers in the pulmonary veins (pulmonary vein isolation [PVI]). Success rates of approximately 75% have been reported in many studies that compared radiofrequency catheter ablation with AADs for the treatment of AF.¹⁷⁻²¹ Still, the role of anticoagulation therapy in preventing atrioembolic stroke after PVI remains unclear and no universally accepted recommendations exist for anticoagulation therapy after successful ablation of atrial fibrillation.

After undergoing radiofrequency ablation of atrial fibrillation, all patients receive oral anticoagulation therapy for a minimum of 3 months (ie, “blanking period”). For those taking warfarin, their INR is monitored to maintain the appropriate therapeutic range (2-3, target 2.5). Following the “blanking period,” considerations for the use of warfarin fall into several categories, with the CHADS₂ or CHA₂DS₂-VASc score commonly used as a predictor of thromboembolic events following catheter ablation of AF.²² For patients with a CHADS₂ or CHA₂DS₂-VASc score of 0, there is general agreement that warfarin therapy may be discontinued after the “blanking period.” On the contrary, for patients with CHADS₂ or CHA₂DS₂-VASc score >1, the recommendations for long-term anticoagulation therapy remain controversial. In many centers, it is common practice to withdraw warfarin, if no symptomatic or asymptomatic arrhythmic recurrences are documented, post-ablation pulmonary stenosis is excluded, and the CHADS₂ score is equal to 1. The results of recent observational trials seem to confirm the value and safety of this strategy.²³⁻²⁷ However, this approach, although reasonable, is substantially empirical and not based on data from randomized clinical trials. In high-risk patients with CHADS₂ score ≥2, different strategies have been used. In a few centers, warfarin is stopped after 3 to 6 months for patients with an apparently successful procedure.²⁸ However in the majority of centers, anticoagulation therapy is continued indefinitely despite the absence of documented atrial fibrillation episodes.

5.2 Rationale

Currently, only limited data regarding the benefit of continuing oral anticoagulation therapy (OAT) in patients who undergo radiofrequency catheter ablation (RFCA), have successful procedures, and remain free from recurrences of atrial fibrillation are available. There are no published, randomized trials regarding continuation or discontinuation of OAT after catheter ablation of AF. Observational or interventional studies that assess OAT withdrawal and OAT continuation do not present a comparison of appropriate patient groups (ie, patients with successful ablation and no OAT are compared to patients on OAT, most or all of whom had early AF recurrence).^{24, 27} Furthermore, most studies used warfarin as OAT and very few thrombotic events were reported for patients with successful ablation, either on or off OAT.^{23, 24, 27} If considering only patients continuing in sinus rhythm (SR), with comparable baseline stroke risk, it is unlikely that these studies^{23, 24, 27, 29} would have detected any difference in event rates between OAT withdrawal and OAT continuation groups. To better understand the effect of OAT withdrawal following successful cardiac ablation, a well-controlled study of subjects at high risk of thromboembolic events that includes an appropriate comparison group and long-term follow-up should be conducted.

The OAT Pilot Study is a randomized, controlled study aimed at understanding the need for continued OAT in high-risk subjects who have successfully undergone cardiac ablation by assessing the risk of thromboembolic events after OAT withdrawal versus OAT continuation.

5.3 Risk Analysis

The risks posed during the conduct of this study are expected to be comparable to those anticipated with the use of OAT according to current AF management guidelines.^{6, 30-33} Anticoagulation therapies have been approved for many decades and the risks and complications are well known. Depending on a patient's risk factors, anticoagulation therapy is recommended for a period of time after undergoing an ablation procedure.³¹ For the OAT Pilot Study, appropriate measures have been implemented to minimize the risk to subjects, while still providing the possible benefits of the two treatment options.

Description and Analysis of Risks:

The OAT Pilot Study will assess the risks associated with subjects randomized to one of two study arms, OAT Withdrawal (Test) Group or OAT (Control) Group. No additional risks are anticipated for subjects randomized to the OAT arm of the study as these subjects will continue with their current physician-prescribed OAT. The major risk for subjects continuing OAT during the Evaluation Period is the risk of major bleeding and hemorrhagic stroke.³¹ The main risks for subjects discontinuing OAT during the Evaluation Period is the increased risk of a thromboembolic event. This risk is higher in subjects with a history or previous thromboembolism, advanced age, hypertension, diabetes mellitus and heart failure.

Minimization of Risks:

The criteria for subject selection, study methods, personnel selection, facilities, and training that have been specified in this study are intended to minimize the risk to enrolled subjects. Subjects will be carefully screened prior to study enrollment to confirm compliance with the study inclusion and exclusion criteria. In addition, prior to randomization, all patients will undergo further AF monitoring to confirm they are AF recurrence free for 3 months following catheter ablation. Once enrolled, additional AF monitoring and clinic follow-up visits are required for each subject to ensure an appropriate level of safety monitoring. Patients experiencing AF recurrence during the study will be treated per the investigator's discretion.

Additionally, safety data will be evaluated periodically during enrollment and follow-up by a physician review committee functioning as a Global Safety Monitoring Committee (GSMC) for this study.

Potential Benefit:

There is no direct benefit expected for subjects enrolled in the OAT arm of the study. Subjects enrolled in the OAT withdrawal arm may experience an increase in their quality of life due to the elimination of complications associated with OAT. Overall, the information gathered during the conduct of this study may be of benefit in the future for the treatment of patients with AF.

6.0 Study Hypothesis

High risk subjects who have successful cardiac ablation and remain free from AF recurrence for 3 months post ablation procedure can discontinue their OAT without an increased risk of thromboembolic events as compared to those who remain on OAT.

7.0 Objective

The objective of this study is to determine the safety of discontinuing oral anticoagulation therapy in high risk patients who have had a successful cardiac ablation and remain AF recurrence free for 3 months post ablation.

8.0 Pilot Study Plan

8.1 Study Design

This is a prospective, multicenter, randomized (1:1), controlled, two-arm, unblinded, pilot study, evaluating the incidence of thromboembolic and hemorrhagic complications after withdrawal of OAT compared to continuation of OAT in subjects who have undergone successful cardiac ablation.

8.2 Treatment Groups

Patients who have undergone successful cardiac ablation for symptomatic AF that are 3 months post procedure (AF recurrences during the 3 month blanking period immediately after cardiac ablation are acceptable), remain free from AF recurrence, fulfill the study inclusion/exclusion criteria, and consent to participate will be considered for study participation and may be enrolled. Enrolled subjects will be randomized (1:1) into one of the two treatment groups described below and participate in the study Evaluation Period (12 months).

- **OAT Withdrawal (Test) Group:** discontinue OAT during the Evaluation Period (from randomization through 12-months follow-up)
- **OAT (Control) Group:** continue OAT during the Evaluation Period (from randomization through 12-months follow-up)

The test group will be compared to the control group in terms of the safety endpoints including the incidence of thromboembolic events or major hemorrhagic complications, minor bleeds, hospitalizations, and all cause mortality. Additional endpoints will be evaluated including QoL, AF recurrence and repeat ablation procedures for AF. Planned statistical analysis of these endpoints is described in the Statistical Analysis Section (13.0) of this protocol.

8.3 Number of Centers

Up to 10 sites will be included in the study. Total subject enrollment is expected to be 100. All subjects enrolled will be followed through 12 months after randomization or until AF recurrence.

8.4 Study Duration, Completion, and Termination

- **Duration:** The study duration is anticipated to be 2 years; 1 year to complete screening/enrollment, and 1 year to complete follow-up for all subjects.
- **Completion:** The study will be considered complete when all subjects either complete their 12-month study visit, withdraw/discontinue the study, become lost to follow-up.
- **Termination:** The study may be terminated prematurely at the discretion of the Sponsor, on statistical grounds, or on the advice/recommendation of the Safety Monitoring Committee. The Sponsor may also terminate a site prior to study completion if it believes the site is no longer capable of participating (eg, cannot fulfill subject enrollment goals, site suspension by IRB or equivalent).

9.0 Subject Selection and Disposition

9.1 Recruitment and Screening Procedures

Patients who have undergone a successful cardiac ablation procedure using devices commercially available and remain AF recurrence free should be screened by the investigator or a member of the designated study staff to determine study eligibility. All high-risk (CHADS₂ ≥ 2 or CHA₂DS₂-VASC ≥

[figure not shown]
3) patients who have had successful cardiac ablation for the treatment of symptomatic AF, remain free from AF recurrence 3-21 months after cardiac ablation may be eligible for inclusion in the study (Refer to Figure 1, Study Flow Chart). A screening log, maintained at each study site, will be used to document the patients reviewed for potential enrollment into the study. The screening log should be completed for any patient considered for study inclusion, regardless of whether the patient is selected or not, as this will allow better management of the study enrollment rate.

9.2 Informed Consent and Enrollment Procedures

If a patient is deemed eligible and is willing to participate in the study, the investigator or designated member of the study staff will properly obtain a written informed consent form (ICF) from the patient prior to study enrollment. The ICF and any revisions must have prior approval of the study site's institutional review board (IRB) or equivalent (eg, ethics committee [EC] or ethics board [EB]).

Patients who sign the informed consent form will be considered enrolled in the study. A sample ICF for this study is provided in a separate document. No patient should undergo any study-specific tests or exams that fall outside the standard of care without first signing the informed consent document for this study. After signing the study's ICF, enrolled subjects will undergo further AF monitoring to confirm freedom from arrhythmia recurrence. Subjects who are deemed free from arrhythmia recurrence and qualify for enrollment according to the study inclusion and exclusion criteria will be randomized to one of the two study arms and followed through the Evaluation Period (12 months).

Figure 1.0 Study Flow Chart

9.3 Study Inclusion Criteria

Candidates for this study must meet **ALL** of the following criteria:

1. Successful cardiac ablation for symptomatic AF refractory to antiarrhythmic drug therapy
2. Documented freedom from AF recurrence (symptomatic or asymptomatic arrhythmic recurrences lasting longer than 30 seconds) 3 months after cardiac ablation (AF recurrence during 3-month blanking period is excluded).
3. Patient must have been on a commercially approved anticoagulation therapy for at least two (2) months prior to randomization in the OAT Study. Commonly prescribed Oral Anticoagulation and Antiplatelet Therapies for use in this study are listed in Appendix A. For patients enrolled in Germany, only those who are prescribed therapies listed in Appendix A can be enrolled in this study.
4. CHADS₂ score ≥ 2 or CHA₂DS₂-VASC ≥ 3
5. Left ventricular ejection fraction $> 25\%$
6. LA size ≤ 65
7. High risk for thromboembolic events (ie, CHADS₂ score ≥ 2 or CHA₂DS₂-VASC ≥ 3 and require OAT before undergoing cardiac ablation)
8. Able and willing to comply with all pre- and follow-up testing and requirements
9. Signed informed consent form
10. Age 18 years or older

9.4 Study Exclusion Criteria

Candidates for this study will be EXCLUDED from the study if **ANY** of the following conditions apply:

1. OAT required for reasons not related to AF (ie, prosthetic valve, PV stenosis, previous pulmonary embolism, presence of spontaneous echo contrast [SEC] at standard echo performed at 3-months follow-up).
2. Any cardiac surgery within the past 60 days (2 months) or valvular cardiac surgical procedure at any time (ie, ventriculotomy, atriotomy, and valve repair or replacement and presence of a prosthetic valve)
3. Previous myocardial infarction (MI), or a percutaneous coronary intervention PCI within the past 3 months
4. Awaiting cardiac transplantation or other cardiac surgery within the next 365 days (12 months)
5. Documented left atrial thrombus
6. Significant pulmonary disease, (eg, restrictive pulmonary disease, constrictive or COPD) or any other disease or malfunction of the lungs or respiratory system that produces chronic symptoms
7. Significant medical problem that in the opinion of the investigator would preclude enrollment in this study
8. Women who are pregnant (as evidenced by pregnancy test if pre-menopausal)
9. Acute illness or active systemic infection or sepsis
10. Unstable angina
11. Contraindication to anticoagulation (ie, heparin, warfarin or another commercially available anticoagulation medication)
12. History of blood clotting or bleeding abnormalities
13. Life expectancy less than 360 days (12 months)
14. Uncontrolled Heart Failure or NYHA Class III or IV heart failure
15. Enrollment in a clinical study evaluating another device or drug, within the past 6 months
16. Unable or unwilling to comply with protocol requirements

9.5 Randomization

All subjects who have signed the study ICF will be required to undergo AF monitoring just prior to randomization. This pre-randomization AF monitoring is designed to verify that the subject is not experiencing symptomatic or non-symptomatic AF recurrence. Pre-randomization AF monitoring will be conducted by Holter Monitor. For subjects with an implantable cardioverter defibrillator (ICD) or artificial cardiac pacemaker, interrogations for the duration of seven (7) days of and within 30 days of randomization will be accepted.

Subjects who are found to be free from AF recurrence during pre-randomization AF monitoring will be randomized (1:1) into one of the two study arms: (1) OAT withdrawal or (2) OAT continuation and followed during the study Evaluation Period (12 months). Randomization will be stratified by gender and region (Europe and North America).

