13.3 Sample Size

A total sample size of 100 (50:50) subjects will be enrolled in this pilot study. This is a pilot study and is not statistically powered to make a statistical inference.

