13.7 Endpoint Analyses

13.7.1 Primary Endpoint Analysis

The primary endpoint is the occurrence of any thromboembolic event or major hemorrhagic complications during the 12-month Evaluation Period.

The Kaplan-Meier method will be used to model the time to the first occurrence of any thromboembolic event or major hemorrhagic complications during the 12-month Evaluation Period following randomization. The survival probabilities of the occurrence of any thromboembolic event or major hemorrhagic complications at the 12 month follow-up along with the corresponding 95% confidence intervals will also be presented. The equality of the survival curves between two randomization groups will be tested by the Log-rank test.

This analysis will include all subjects in the analysis population and account for censored observations. Subjects lost to follow-up, withdrew or discontinued prior to reaching their primary endpoint will be censored at their last visit.

Descriptive statistics such as 25th percentile, median and 75th percentile of time to the first occurrence as well as the 95% confidence intervals around the median time will be presented overall and by randomization groups.

The number and proportion of subjects experiencing occurrence of any thromboembolic event or major hemorrhagic complications will be summarized overall and by two randomization groups at 12 month follow up. The Fisher exact test will be used to compare the proportions between the two randomization groups.

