13.7.2 Analysis of Secondary Endpoints

Descriptive statistics including frequency and percentage for categorical secondary endpoints will be presented. The categorical secondary endpoints include minor hemorrhagic events (minor bleeds), hospitalization with any thromboembolic or major hemorrhagic event, all cause mortality, AF recurrence and repeat ablation procedures for AF.

The 95% confidence intervals for binary outcome will be computed using exact binomial method. Descriptive statistics and 95% confidence intervals will be presented overall and by randomization groups. The proportion of the occurrence will be compared between randomization groups using the Fisher exact test.

Descriptive statistics for continuous endpoints will include number of subjects, mean, standard deviation, median, 25th and 75th percentiles, minimum and maximum. These continuous secondary endpoints include the index scores of the SF-36. Change from baseline for the index score of the SF-36 will be compared between two randomization groups using the Wilcoxon rank sum test.

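### Randomization is stratified by gender and region, but no between-arm test uses the strata, so the tests are somewhat conservative if either factor predicts outcome

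*Combined protocol and SAP*

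**What the plan says.** Section 9.5 (Randomization) states that subjects "will be randomized (1:1) into one of the two study arms" and adds: "Randomization will be stratified by gender and region (Europe and North America"). Two factors at two levels give four strata.

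No between-arm comparison in Section 13 names these factors:

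- **Primary endpoint, time to event (13.7.1):** "The equality of the survival curves between two randomization groups will be tested by the Log-rank test".
- **Primary endpoint, proportion (13.7.1):** "The Fisher exact test will be used to compare the proportions between the two randomization groups".
- **Binary secondary endpoints (13.7.2):** "The proportion of the occurrence will be compared between randomization groups using the Fisher exact test".
- **SF-36 (13.7.2):** a Wilcoxon rank sum test on change from baseline, with no strata or covariates.

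Gender returns only in the disposition summary (13.5) and the baseline table (13.6). Region does not reappear in Section 13. No reason is given for leaving the factors out.

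The planned intervals are for the 12-month survival probabilities ("at the 12 month follow-up along with the corresponding 95% confidence intervals will also be presented"), for the median time to event, and for binary proportions overall and by group. None is for a difference or ratio between arms. On size, Section 13.3 says: "A total sample size of 100 (50:50) subjects will be enrolled in this pilot study", and "This is a pilot study and is not statistically powered to make a statistical inference".

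**The concern.** Stratified allocation forces the arms to be nearly balanced on gender and region. If those factors predict outcome, the arm difference varies less from trial to trial than it would under simple randomization. A test that ignores the strata still charges the full variance, so it rejects less often than its nominal level and gives up some power. The design has gone to the trouble of balancing the factors, and the analysis does not collect the benefit. At stake is a modest amount of sensitivity, mainly for the secondary endpoints that yield more information than the rare primary events.

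**Working it through.** **Plan's own figure.** The total of 100 comes with no event rate, effect, margin, significance level or power, so there is no calculation to reproduce. The documents supply 1:1 allocation, 100 subjects, four strata and 12 months of follow-up. Everything else below is assumed: stratum sizes, blocks of 4, event rates and stratum effects.

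**Formula.** If the strata explain a share R² of outcome variance, the arm contrast has about (1 − R²) of the variance that the unstratified test uses. The true level of a nominal two-sided 5% test is then

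2 × [1 − Φ(1.96 / √(1 − R²))].

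**Primary endpoint, analytic check.** Take two equal strata, overall rate p and risk ratio k between them, so the stratum rates are 2p/(1+k) and 2pk/(1+k). With p = 5% and k = 4 these are 2% and 8%.

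- Within-stratum variance: ½(0.02×0.98 + 0.08×0.92) = 0.0466.
- Naive variance: 0.05×0.95 = 0.0475.
- Ratio 0.981, true level 4.8%.
- Over p = 3% to 5% and k = 2 to 4 the level runs from 5.0% to 4.8%. At p = 10% it runs from 4.9% to 4.6%.

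**Primary endpoint, log-rank simulation.** Strata of 36/14/34/16, 30% early censoring, 4,000 trials per row. The rates were chosen with the background bleeding and stroke rates in Section 5.1 in mind. Entries are % rejected, unstratified / stratified.

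| 12-month rate | Stratum HR per factor | No arm effect | Arm HR 3 |
|---|---|---|---|
| 3% | 2 | 1.8 / 1.6 | 17.1 / 17.2 |
| 3% | 4 | 1.7 / 1.8 | 17.1 / 18.3 |
| 5% | 2 | 4.0 / 4.0 | 28.6 / 28.7 |
| 5% | 4 | 3.3 / 4.1 | 25.5 / 28.4 |
| 10% | 2 | 4.5 / 4.6 | 50.9 / 52.4 |
| 10% | 4 | 3.8 / 4.5 | 43.0 / 50.2 |

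A visible gain needs a hazard ratio of 4 for each factor. Sparse events matter far more: with 50 per arm, the exact size of Fisher's test is 0.2%, 0.7% and 1.8% at rates of 3%, 5% and 10%, with no stratum effect at all.

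**AF recurrence.** Assume rates of 10%, 20%, 30% and 40% in four strata of 25.

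- Mean rate 0.25; variance between strata (0.15² + 0.05² + 0.05² + 0.15²)/4 = 0.0125; total variance 0.25×0.75 = 0.1875.
- R² = 0.0125/0.1875 = 6.7%. True level = 2 × [1 − Φ(1.96/√0.933)] = 4.2%.

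Simulation (6,000 trials) with an unstratified chi-square added, so that the effect of stratifying is separated from the effect of changing the test:

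| | Fisher | Unstratified chi-square | CMH |
|---|---|---|---|
| Type I error | 3.0% | 4.2% | 4.7% |
| Power, odds ratio 3 | 61.1% | 67.1% | 69.7% |
| Power, odds ratio 3, all strata at 25% | 69.0% | 73.4% | 73.4% |

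Of the 8.6-point gap between Fisher and CMH, 6.0 points are Fisher's discreteness and 2.6 come from stratifying. A further set of runs gave 60%, 67% and 69%, which puts the stratification gain at 2 points. The last row shows a 4.4-point gap even when the strata predict nothing. With a milder gradient (20/25/25/30%), R² is 0.00125/0.1875 = 0.7%, the level is 4.9%, and unstratified chi-square and CMH have equal power (74.0% and 73.9%).

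**SF-36 change.** Strata as in the log-rank simulation, 6,000 trials, Wilcoxon test.

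| Shift per factor | R² | Simulated level | Formula |
|---|---|---|---|
| 0.25 SD | 3% | 4.8% | 4.7% |
| 0.5 SD | 11% | 3.9% | 3.8% |
| 1.0 SD | 32% | 1.4% | 1.7% |

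With no shift the simulated level was 5.2%; the simulation standard error near 5% is √(0.05×0.95/6000) = 0.3 points. So the first row cannot be told apart from 5%.

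**The case against.** The best defence is that nothing would turn on this. Section 13.3 disclaims statistical inference. An error in the conservative direction cannot create a false positive, and the secondary endpoints carry no decision rule. Nothing in the documents shows that gender or region predicts any of these outcomes. SF-36 is analysed as change from baseline, which already removes stable level differences between the sexes or regions, so a loss remains only if the change itself differs by stratum. With a handful of primary events over four strata, a stratified hazard ratio may be unstable.

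All of this stands as an argument about size and priority. It does not remove the point: the plan still specifies these tests and is silent on its own design factors.

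Three stronger readings are tempting, and the documents do not support them:

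- **The confidence intervals are too wide.** A reader might infer this from the variance argument. But the plan contains no between-arm interval, and stratified allocation reduces the variance of the arm contrast, not that of a single-arm estimate.
- **Stratifying would raise power for AF recurrence from about 60% to 69%.** That compares Fisher with CMH and mixes two changes; most of the gap is Fisher's discreteness.
- **The conservatism would hide harm from withdrawal.** Section 13.1 does state a non-inferiority aim, which makes a loss of sensitivity unwelcome. For the primary endpoint, though, the part due to ignoring the strata is negligible beside the effect of few events.

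**Conclusion.** The mismatch between design and analysis is a matter of text and is certain. Its consequence is conditional: the tests are somewhat conservative if gender or region is prognostic, and unaffected if not. The loss is negligible for the primary endpoint short of very strong stratum effects. It is modest for AF recurrence (level about 4.2%, 2 to 3 points of power) under a gradient that is itself steep. For SF-36 change it ranges from nothing measurable to substantial, depending on how far the change differs by stratum. All these sizes rest on assumed stratum effects and stratum sizes. This is a low-priority correction that would not alter the conclusion of an unpowered pilot.

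**What to change.** - **13.7.1:** make the log-rank test stratified by gender and region.
- **13.7.2, binary endpoints:** use a CMH test over the same strata, in its exact form when cells are sparse.
- **13.7.2, SF-36:** adjust the comparison of change for gender and region, by a stratified Wilcoxon test or by covariates.
- Keep the unstratified tests as sensitivity analyses.
- If a between-arm estimate is added, base it on the same strata.

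The cost is SAP wording only, since both factors must already be recorded in order to randomize. The downside is small: strata without events contribute nothing to the test, and a stratified hazard ratio may be unstable with few primary events. If the sponsor prefers to leave the strata out, the SAP should say so and give the reason.
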